8.9 Interim Analyses

Interim analyses will be conducted after the enrollment of 200 patients, 350 patients, 550 patients and 650 patients.

After the enrollment of 200 and 350 patients an interim analysis will be conducted applying a criterion for potentially *stopping for futility*. A non-binding recommendation to stop patient enrollment for futility will be given if interim results are not in a “promising zone” to reach the CAE30 success criterion. More specifically, the stopping recommendation will be given if the posterior predictive probability of CAE30 success (i.e., proving non-inferiority) with the maximum number of 700 patients is below a specific futility cut-off $\Theta_{F_N} = 0.1$ with $N = 200$ or 350 representing the respective enrollment status:

Probability(CAE30 success with 700 patients | interim data) $< \Theta_{F_N}$, i.e.

Probability(Posterior predictive probability($p_{PCT} < p_{ctrl} + 0.1$, 700 patients | interim data) $> 98.5\%^1$) < 0.1

After the enrollment of 550 and 650 patients an interim analysis will be conducted applying criteria to stop potentially (a) for futility or (b) for study success:

a. *Stopping for futility:*

A non-binding recommendation to stop patient enrollment for futility will be given if interim results are not in a “promising zone” to reach the CAE30 success criterion. More specifically, enrollment will be stopped if the posterior predictive probability of CAE30 success with the maximum number of 700 enrolled patients is below a specific futility cut-off $\Theta_{F_N} = 0.1$ with $N = 550$ or 650 representing the respective enrollment status:

Probability(CAE30 success with 700 patients | interim data) $< \Theta_{F_N}$, i.e.

Probability(Posterior predictive probability($p_{PCT} < p_{ctrl} + 0.1$, 700 patients | interim data) $> 98.5\%^1$) < 0.1

b. *Stopping for success:*

Enrollment will be stopped for success if interim results reveal a sufficiently high probability that success criteria are reached for the endpoints CAE30, shortABx and prescribedABx. More specifically, enrollment will be stopped if the posterior predictive probabilities of the three endpoints CAE30, shortABx and prescribedABx for the respective number

of enrolled patients are above the cut-off $\Theta^s_N = 0.9$:

Probability(CAE30 success with enrolled patients | interim data) > Θ^s_N AND
Probability(shortABx success with enrolled patients | interim data) > Θ^s_N AND

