The protocol changes required a re-specification of the analysis parameter γ to assure type-I error rate control at 2.5% (new order of hierarchical testing of endpoints: first shortABx, then CAE30, then prescribedABx; null hypothesis for shortABx instead of CAE30; interim and final CAE30 NI analyses on PP populations; interim analyses with 550 and 650 patients). Under the null for the primary study endpoint shortABx (relative risk of shortABx for PCT arm versus Control arm set to 1) and under the additional conservative assumptions of effects of CAE30 and prescribedABx as in the pilot study ($RR_{CAE30} = 0.30$, $RR_{prescribedABx} = 0.60$; PCT arm versus Control arm) and the PP population as a random subset of 50% of the patients of the full population (50% estimated for the running study), a γ value of 0.985 was determined to keep the type-I error rate below 2.5% (increase of γ vs. previous protocol version from 0.9785 to 0.985; γ estimated by linear regression of type-I error rate vs. specified γ values based on Monte Carlo runs with 50,000 simulated clinical trials).

Moreover, simulations showed that adequate statistical power could be achieved even for small CAE30 effects. Assuming (a) half of the shortABx effect observed in the pilot study ($RR_{shortABx} = 1.9$), (b) only one tenth of the CAE30 effect observed in the pilot study ($RR_{CAE} = 0.9$), (c) half the prescribedABx effect observed in the pilot study ($RR_{prescribedABx} = 0.80$), and (d) the PP population as a random subset of 50% of the patients of the full population (50% PP patients estimated for the running study), we obtained 99% statistical power for shortABx superiority on ITT population, 75%

for CAE30 non-inferiority on PP population, and 48% for prescribedABx superiority on ITT population. The following Table 2.6 gives an overview of the study design characteristics of this scenario.

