Probability(Posterior predictive probability($p_{PCT} < p_{ctrl} + M$, 700 patients | interim data) > γ) < Θ^F , with $\gamma = 0.985$ and $M = 0.1$ (10% non-inferiority margin).

b. Stopping for success

Enrollment will be stopped for success if interim results reveal a sufficiently high predictive probability that success criteria can be reached for the endpoints CAE30, shortABx and prescribedABx with the currently enrolled patients. More specifically, enrollment will be stopped if the posterior predictive probabilities of the three endpoints CAE30, shortABx and prescribedABx for the respective number of enrolled patients are above the specific success cut-off $\Theta^S = 0.9$:

Probability(CAE30 success with enrolled patients | interim data) > Θ^S AND

Probability(shortABx success with enrolled patients | interim data) > Θ^S AND

Probability(prescribedABx success with enrolled patients | interim data) > Θ^S .

Note: A final analysis will still be conducted following an early stopping decision at any interim after all enrolled patients have completed their respective follow-up of 30 days.

Note: Use of the posterior predictive probability will allow to conduct the interim analysis in a timely manner without the need to wait for the completion of the 30 days follow-up times of all patients. Thereby, missing or incomplete endpoint data of enrolled patients will be imputed by predicted endpoint data including its respective level of uncertainty.

Posterior predictive probabilities for the safety endpoint CAE30 will be calculated as follows:

1. Computation of predictive distributions:

a. For patients still to be enrolled for a maximum of 350 + 350 study patients the following equation will be used to determine the beta-binomial predictive distribution (see e.g. [Cowles2013] p. 62, or [Rajat2021] section 3.1):

$$BBP(x'_i | n'_i, x_i, n_i) = \binom{n'_i}{x'_i} \frac{Beta(x'_i + x_i + 1, n'_i - x'_i + n_i - x_i + 1)}{Beta(x_i + 1, n_i - x_i + 1)} \quad (1)$$

with

i : index for study arm (“PCT arm” or “Control arm”),

n'_i : number of patients still to be enrolled for study arm i ,

i.e. 350 – number of patients enrolled for study arm i until interim analysis,

x'_i : number of patients with events among the n'_i patients still to be enrolled for study arm i ,

n_i : number of patients of study arm i with complete follow-up data,

x_i : number of patients of study arm i with complete follow-up data and observed events,

$Beta(,)$: beta function.

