b. For already enrolled patients with partial follow-up data and no observed CAE30 yet, the following equation (2) will be applied with variables ... depending on follow-up time to determine the beta-binomial predictive distribution (analogous to (a) but with interim data adequately conditioned on follow-up time, see e.g. [Rajat2021] section 3.2):

$$BBP(x'_{i(t_j)} | n'_{i(t_j)}, x_{i(t_j)}, n_{i(t_j)}) = \binom{n'_{i(t_j)}}{x'_{i(t_j)}} \frac{Beta(x'_{i(t_j)} + x_{i(t_j)} + 1, n'_{i(t_j)} - x'_{i(t_j)} + n_{i(t_j)} - x_{i(t_j)} + 1)}{Beta(x_{i(t_j)} + 1, n_{i(t_j)} - x_{i(t_j)} + 1)} \quad (2)$$

with

i : index for study arm ("PCT arm" or "Control arm"),

$t = (t_1, t_2, \dots, t_p)$: vector of p distinct partial follow-up times (in days, $t_p < 30$),

$n'_{i(t_j)}$: number of enrolled patients of study arm i with partial follow-up data and without event until time t_j ,

$x'_{i(t_j)}$: number of patients with events after time t_j among the $n'_{i(t_j)}$ patients of study arm i with partial follow-up data and without event until time t_j ,

$n_{i(t_j)}$: number of patients with complete follow-up data and without event until time t_j ,

$x_{i(t_j)}$: number of patients with events after time t_j among the $n_{i(t_j)}$ patients with complete follow-up data without event until time t_j ,

$Beta(,)$: beta function.

The main idea behind this computation is to apply the equation (1) presented in a. in order to compute time-dependent posterior probabilities and posterior predictive probabilities that depend on the follow-up times of adequately censored patients (the more follow-up time has already passed, the less likely it is to still observe an event).

2. With the predictive distributions we will conduct Monte Carlo simulations, e.g. simulate the number of adverse events per study arm for many (e.g. 1e6) trials with maximum number of 350 + 350 patients. The number of events per study arm is the sum of three components: (i) the number of already observed events, (ii) the number of events predicted for patients yet to be enrolled and (iii) the number of events predicted for patients with partial follow-up data. The number of events according to (i) is fixed for all trials while the number of events according to (ii) and (iii) varies between trials and is sampled according to the posterior predictive distributions.

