3. The posterior predictive probability of study success is estimated by the proportion of simulated trials with 350 patients enrolled per study arm meeting study success criteria with $\gamma = 0.985$.

Analogous computations will be conducted for the other two main study endpoints shortABx and prescribedABx.

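### The binding success stop is defined for the patients already enrolled, but the only computation the SAP writes projects to 350 per arm; coded literally, the trial would stop early less often than the stated rule, a conservative error

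*SAP*

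**What the plan says.** **The rule.** SAP 2.5(b) stops enrollment at 550 or 650 when it is sufficiently probable that "success criteria can be reached for the endpoints CAE30, shortABx and prescribedABx with the currently enrolled patients". The formal version requires the three predictive probabilities "for the respective number of enrolled patients are above the specific success cut-off" of 0.9. Protocol 8.9(b) has the same horizon, for example "Probability(shortABx success with enrolled patients | interim data". SAP 2.6 calls this criterion binding and the futility criterion non-binding.

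**The computation.** SAP 2.5 then gives one numbered procedure, introduced for CAE30.
- Step 1a is headed "For patients still to be enrolled for a maximum of 350 + 350 study patients" and sets the number of future patients in each arm to 350 minus those enrolled.
- Step 1b predicts outcomes for enrolled patients with partial follow-up.
- Step 2 simulates "trials with maximum number of 350 + 350 patients", summing observed events, predicted events in future patients (component ii) and predicted events in enrolled patients with partial follow-up.
- Step 3 says the predictive probability is "estimated by the proportion of simulated trials with 350 patients enrolled per study arm meeting study success criteria" with γ = 0.985.

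The section closes: "Analogous computations will be conducted for the other two main study endpoints shortABx and prescribedABx".

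**Futility.** The futility rule uses CAE30 alone and asks about success with 700 patients.

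**Stated performance.** Table 2.6 gives a success stop of 27% at 550, 12% at 650 and 39% in total, with success probabilities of 99%, 75% and 48% for shortABx, CAE30 and prescribedABx.

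**The concern.** Steps 1a, 2 and 3 compute what the futility rule needs. No version is written without future patients, so the success rule has no computation of its own. For shortABx and prescribedABx the mismatch is plainest: neither has a futility rule, so the success stop is the only use of their predictive probabilities, yet the steps they inherit end at 350 per arm.

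The written horizon also does not fit the decision. Under SAP 2.6, the final analysis after a stop covers the patients enrolled until the stop takes effect. A projection to 350 per arm forecasts a 700-patient result that the stop itself would prevent.

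At stake is a binding decision. Two programmers following different paragraphs of SAP 2.5 could reach opposite answers from the same interim data. The threshold is also tied to the simulated design: a "value of 0.985 was determined to keep the type-I error rate below 2.5"%, so the rule executed should be the rule simulated.

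**Working it through.** **Inputs** (SAP 2.3.3 and Table 2.6): marginal rates 22% shortABx, 20% CAE30, 40% prescribedABx; relative risks 1.9, 0.9, 0.8; margin 0.10; γ = 0.985; PP a random half; 1:1 allocation, so 275 per arm at 550 and 350 at 700.

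**Arm rates.** Control = 2 × marginal / (1 + RR); PCT = RR × control.
- shortABx: 0.44/2.9 = 15.2% control, 28.8% PCT
- CAE30: 0.40/1.9 = 21.1% control, 18.9% PCT
- prescribedABx: 0.80/1.8 = 44.4% control, 35.6% PCT

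**Reproducing the plan.** With a one-sided normal approximation at z = 2.170 (the 0.985 quantile), final-analysis power is 98.7% for shortABx (350 per arm) and 74.6% for CAE30 (175 per arm, unpooled). Table 2.6 totals are 99% and 75%.

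**Closed-form check at 550, no data pending, endpoints independent.**

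1. *Stated rule.* With complete data it reduces to Z > 2.170 for each endpoint. Pass probabilities are 95.7%, 63.5% (138 PP patients per arm) and 48.3%. Product: 0.957 × 0.635 × 0.483 = 29%.
2. *Written steps.* Let f = 275/350 = 0.786. With a flat prior, the predicted final Z is approximately normal with mean Z/√f and variance (1 − f)/f. A predictive probability above 0.9 then needs Z > √f × 2.170 + 1.282 × √(1 − f) = 0.886 × 2.170 + 1.282 × 0.463 = 2.517. That is a current posterior probability of about 0.994 instead of 0.985. Pass probabilities become 91.4%, 49.9% and 34.8%. Product: 0.914 × 0.499 × 0.348 = 16%.

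**Simulation of the Table 2.6 scenario.** One patient per day; five follow-up days for the last patient; Beta(1,1) posteriors; beta-binomial prediction; both horizons applied to the same trials. Assumed, not in the documents: CAE30 event timing; the length-of-stay rate of 0.12 read as per day; independent endpoints unless stated.

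| Assumption | Stop at 550, enrolled rule | Stop at 550, written steps | Ratio |
|---|---|---|---|
| SAP Table 2.6 | 27% | – | – |
| CAE30 event-time rate 0.12 per day | 24.7% | 15.7% | 0.64 |
| CAE30 event-time rate 0.3 per day | 26.4% | 15.5% | 0.59 |
| Rate 0.12, shortABx–prescribedABx correlation −0.5 | 24.2% | 15.8% | 0.66 |
| Rate 0.12, correlation −0.8 | 24.5% | 16.4% | 0.67 |
| Simplified pending data (13 per arm CAE30, scaled to PP; 4 per arm antibiotic endpoints) | 22% | 16% | 0.73 |

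With no pending data the simulated enrolled rule stops 29.7% at 550, close to the closed form, and the ratio is 0.52.

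Over the full-simulation runs with pending data, the enrolled rule stops 36–39% early in total; the written steps stop 26–29%. The 0.3-per-day run under the enrolled rule gives 26.4% at 550, 12.6% at 650, 39.0% in total, and success probabilities of 98.9%, 75.9% and 47.4%, all within 1 point of Table 2.6. No run of the written steps reaches 27% or 39%. Table 2.6 therefore appears to describe the enrolled-patient rule.

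**Cost in this scenario.** Mean enrollment: 657 versus 670 (rate 0.12), 654 versus 670 (rate 0.3), 660 versus 670 (simplified). prescribedABx power: 47.3% versus 45.3% (rate 0.12) and 47.4% versus 44.7% (rate 0.3). No simulated trial met the written criterion at 550 or 650 without also meeting the enrolled-patient one. About 99% of trials stopped at 550 under the enrolled rule later succeed on all three endpoints, so the longer horizon gains almost nothing in reliability.

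**Other effect sizes** (simplified pending data; RR shortABx/CAE30/prescribedABx; stop at 550, enrolled rule versus written steps).
- 1.9/0.5/0.8: 40% versus 30%
- 1.9/0.65/0.7: 74% versus 65%
- 2.74/0.30/0.61 (about the pilot effects): 99% versus 98%

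**The case against.** The strongest reply is that the rule itself is never in doubt. Both documents tie success to enrolled patients, repeatedly, and both note that incomplete data of enrolled patients will be imputed, for which step 1b already supplies the CAE30 equation. The numbered steps are introduced for CAE30 and match the 700-patient futility rule, and analogous need not mean identical. A careful programmer would adapt the horizon, and Table 2.6 suggests that whoever ran the simulations did.

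Much of this stands. The intended horizon is clear, and nothing in the documents shows that interim code uses the other one. A reader might infer that the trial will in fact stop a third less often than planned, or that Table 2.6 is wrong. The documents support neither: the loss arises only if the steps are coded literally, and the table fits the stated rule.

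It does not remove the defect. If the steps are for futility only, the binding stop has no written computation, and the sentence extending them to the two antibiotic endpoints lacks a matching procedure. Step 3 followed literally gives a different decision from the rule stated above it, so this is a conflict within the section as well as missing detail.

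**Conclusion.** The point holds as a conflict between the stated success rule and the only written computation. Coded as written, the stop at 550 would fire in about 15–16% of trials in the Table 2.6 scenario, against 22–26% under the stated rule with pending follow-up: roughly 30–35% fewer in most runs, with 27% and 41% at the edges of the pending-data assumptions tried. The figure belongs to that scenario. At stronger effects the relative loss is about 12–25%, and about 1% at the pilot effects, so a general loss of a third should not be inferred.

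Nor should a threat to error control. The longer horizon asks for stronger evidence before stopping (Z of about 2.52 instead of 2.17 at 550), so type-I error is not inflated. In the Table 2.6 scenario the cost is 1–3 points of prescribedABx power and about 10–16 more patients on average. The sizes rest on the assumed CAE30 event timing, the length-of-stay rate read per day, and PP as a random half. This is worth correcting because the criterion is binding and the correction is cheap; no conclusion of the trial is endangered.

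**What to change.** In SAP 2.5, separate the two computations.

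- **Futility (CAE30, all four looks):** keep steps 1a to 3, projected to 350 per arm.
- **Success (550 and 650, all three endpoints):** set n′ = 0, that is, omit step 1a and component ii of step 2. Impute only enrolled patients with incomplete data. Count success at the number currently enrolled per arm, using the PP subset for CAE30.

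Reword the closing sentence so that shortABx and prescribedABx refer to the success computation only, and confirm that the interim code matches. The cost is a few lines of text and a matching line of code, with no new data and no change to γ or the 0.1 and 0.9 cut-offs.

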Table 2.6: Characteristics of the study design with protocol changes (sABx as primary endpoint, CAE30 non-inferiority testing with 10% NI margin, IA with 550 and 650 patients, and $\gamma = 0.985$) assuming (a) half the effect observed in the pilot study for shortABx ($RR_{shortABx} = 1.9$), (b) only one tenth of the CAE30 effect observed in the pilot study ($RR_{CAE} = 0.9$), (c) half the effect observed in the pilot study for prescribedABx ($RR_{prescribedABx} = 0.80$), and (d) the PP population as a random subset of 50% of the patients of the full population. Interim, final and total results in rows, first two columns to describe the level of analysis, columns three to five for the probabilities of meeting endpoint-specific study success criteria (hierarchical testing: (1) shortABx superiority on ITT population, (2) CAE30 non-inferiority on PP population, (3) prescribedABx superiority on ITT population, columns six to eight for outcomes of interim analyses.

Abbreviations: “IA” for “interim analysis”, “IA-200” for “IA with 200 enrolled patients”, “End-700” for “final analysis with 700 enrolled patients”, “-” for “not applicable” and “recom.” for “recommendation”.

Level of Analysis		Results						
Stage of Analysis	# PP Patients	Probability of Meeting EP Success Criteria			Interim Analysis Outcome			Efficacy
		sABx	CAE30	pABx	Futility recom.	Study stopped		
IA-200	100	-	-	-	7%	-	0%	
IA-350	176	-	-	-	8%	-	0%	
IA-550	276	27%	27%	27%	12%	27%	27%	
IA-650	324	12%	12%	12%	15%	12%	12%	
End-700	350	59%	36%	9%	-	-	-	
Total	-	99%	75%	48%	-	39%	39%	

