2.6 Timing of Final Analysis

A maximum number of 700 patients will be enrolled. The study may be stopped earlier due to futility (non-binding criterion) or success (binding criterion) after interim analyses with about 200 patients, 350 patients, 550 patients and 650 patients (see previous section for more information). In any case the final analysis will be conducted comprising all patients enrolled into the study until the implementation of study stop. The final analysis will be conducted with complete 30 day follow-up data of all enrolled patients.

3 Study Population

Hospitalized adult patients with suspected or confirmed pneumonia at time of admission or while admitted to the ED who are prescribed antibiotics (including septic patients with respiratory focus) are enrolled into the study. Please refer to the study protocol for additional medical information, e.g. concerning eligibility criteria (inclusion and exclusion criteria in Section 4.2.1 and 4.2.2 of the protocol, respectively).

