3.1 Analysis Populations

The intention-to-treat (“ITT”) patient population will comprise all randomized non-COVID-19 patients. The per-protocol (“PP”) patient population will comprise all ITT patients (a) fulfilling study inclusion criteria, (b) not meeting study exclusion criteria at enrollment, (c) even if meeting study exclusion criterion after enrollment or meeting a pre-defined overruling criterion, (d) with PCT measurements performed daily in the first week and thereafter at least every 48 hours during antibiotic treatment, (e) ~~-if assigned to PCT group, antibiotic steward~~ ship team recommendation given to the treating physician on enrollment day and for each PCT measurement taken Monday-Friday described under d) and antibiotics stopped according to the PCT algorithm. An exception will be made if the ASP decides the patient will be given the same recommendation throughout their hospitalization.

Consequently, it should be noted that ASP recommendations should also be provided for patients meeting pre-defined overruling criteria (e.g., need for ICU care) since such patients may still qualify for the per-protocol population.

Patients of the PCT arm who are discharged before that day’s PCT has resulted will be excluded from the per protocol population. Patients in the PCT arm who were continued on antibiotics despite a weekend/holiday/no ASP member available PCT value that would have resulted in an ASP recommendation to stop antibiotics will also be excluded from the per protocol population. Patients in the PCT arm whose antibiotics were discontinued despite weekend/holiday/no ASP member available PCT value that would have resulted in continuation of antibiotics will also be excluded.

(f) if assigned to control group, no PCT measurements to treating physician during index hospitalization.

Primary analysis of the superiority endpoint “antibiotic exposure” will be conducted on the basis of the ITT patient population. Analysis of the non-inferiority endpoint “composite adverse events until

day 30" will be conducted on the basis of PP and ITT patient population. PP-results will be compared and discussed with corresponding results obtained for ITT patient population.

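### SAP 2.5's interim recipe for CAE30 has no per-protocol step and projects to 350 per arm, although non-inferiority is tested on about 175 per arm

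*SAP*

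**What the plan says.** The worked steps in SAP 2.5 begin with a beta-binomial prediction "For patients still to be enrolled for a maximum of 350 + 350 study patients". The number still to come in each arm is 350 minus those enrolled, and the observed data are all patients of the arm with complete follow-up. Step 1b adds every enrolled patient with partial follow-up. Step 2 simulates "trials with maximum number of 350 + 350 patients", and step 3 takes the "proportion of simulated trials with 350 patients enrolled per study arm meeting study success criteria". None of these steps mentions PP, and Protocol 8.9 names no population either.

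Elsewhere the population is stated. SAP 2.3.3 lists "interim and final CAE30 NI analyses on PP populations" among the conditions under which γ was reset to 0.985. The Table 2.6 caption specifies "CAE30 non-inferiority on PP population", and the table gives 276, 324 and 350 PP patients at 550, 650 and 700. SAP 4.5 and Protocol 8.6.3 base the CAE30 test on PP, with ITT as a second analysis. Yet SAP 4.5 also describes the CAE30 denominators as the numbers randomized.

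The success rule in SAP 2.5 requires that predictive probabilities "for the respective number of enrolled patients are above the specific success cut-off", so it concerns patients already enrolled. SAP 2.6 labels the two kinds of stop "futility (non-binding criterion) or success (binding criterion".

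**The concern.** A script that follows SAP 2.5 to the letter does not carry out the design that was simulated. There are two ways to go wrong:

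- **Hybrid reading.** The analyst takes PP interim data from SAP 2.3.3 but still adds every future patient, 75 per arm at 550 or 25 at 650, when about half of them are expected to be PP.
- **All-patient reading.** The analyst uses all patients throughout and projects to 350 per arm.

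Both assume more CAE30 information than the PP test will have. While the observed PCT excess is small relative to the 10-point margin, this raises the predictive probability and mutes the futility advice. The version history in the SAP shows that the 350-patient look has taken place, so the looks at stake are 550 and 650.

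The success stop is the more serious exposure because it is binding. The worked steps cover only the 350 + 350 projection, so nothing shows the calculation for enrolled patients or names the population for each endpoint. If CAE30 is evaluated there on all enrolled patients, enrollment can end with too few PP patients for the PP test. The final analysis still follows, but those patients cannot be recovered.

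**Working it through.** **Inputs.** From SAP 2.5: margin M = 0.10, γ = 0.985, futility cut-off 0.1, success cut-off 0.9. From SAP 2.3.3: a random 50% of patients are PP, and rates follow from the marginal rate and RR.

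- CAE30, 20% marginal, RR 0.9: control 0.40/1.9 = 21.1%, PCT 18.9%.
- shortABx, 22% marginal, RR 1.9: control 0.44/2.9 = 15.2%, PCT 28.8%.
- prescribedABx, 40% marginal, RR 0.8: control 0.80/1.8 = 44.4%, PCT 35.6%.

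PP patients per arm are half the Table 2.6 counts: 50, 88, 138 and 162 at the interims and 175 at the end.

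**Step 1: reproduce the stated 75% CAE30 power.** Power ≈ Φ[(M + pC − pT)/SE − z(0.985)], with SE² = [pC(1−pC) + pT(1−pT)]/n. The numerator is 0.1 + 0.2105 − 0.1895 = 0.121, and the bracket is 0.1662 + 0.1536 = 0.3198.

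- n = 175: SE = 0.0427; 2.83 − 2.17 = 0.66; power 74.6% (exact Bayesian criterion 74.9%).
- n = 350: SE = 0.0302; 4.00 − 2.17 = 1.83; power 96.7%.

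The plan's 75% therefore corresponds to 175 per arm.

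**Step 2: futility rates.** Exact beta-binomial prediction with uniform priors; success is P(pPCT < pCtrl + 0.1) > 0.985; futility is advised if the predictive probability is below 0.1. Interim outcomes are taken as complete.

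| Reading | Size per arm at 550, projected to | 200 | 350 | 550 | 650 |
|---|---|---|---|---|---|
| Table 2.6 | – | 7% | 8% | 12% | 15% |
| PP projection | 138 → 175 | 8.2% | 8.2% | 11.9% | 16.4% |
| Hybrid | 138 → 138 + 75 = 213 | 2.9% | 3.9% | 6.0% | 11.9% |
| All patients | 275 → 350 | 2.0% | 1.4% | 1.3% | 1.6% |

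At RR 1.0 the 550/650 rates are 23/31% (PP), 13/24% (hybrid) and 5/7% (all patients). If the PP fraction is 40% to 63% (assumed range; the pilot had 60/95 = 63%), PP futility at 550 runs from 17% to 7%, and the hybrid from 8% to 4%.

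**Step 3: where the advice changes.** At 550, with 28/138 control PP events (all-patient column: both counts doubled, on 275 per arm), the predictive probabilities are:

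| PCT events of 138 | PP | Hybrid | All patients |
|---|---|---|---|
| 33 (excess 3.6 points) | 0.08 | 0.22 | 0.40 |
| 34 | 0.04 | 0.15 | 0.24 |
| 35 (excess 5.1 points) | 0.02 | 0.101 | 0.12 |

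On PP the advice is to stop in all three rows; on the other readings it is to continue. At 32 all three readings continue; at 36 all three advise stopping.

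**Step 4: success stop.** 200,000 simulated trials, looks at 550 and 650, enrolled patients only, shortABx and prescribedABx on ITT. The documents do not give event timing for the updated simulation, so two extremes were run: outcomes known at once, and 12 patients per arm wholly unobserved. The second follows from one patient per day with five follow-up days of the last patient, which leaves about 25 incomplete.

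| CAE30 population at the interim | Stop at 550 | Stop at 650 | PP CAE30 test unmet among 550 stops | Power shortABx/CAE30/prescribedABx |
|---|---|---|---|---|
| Table 2.6 | 27% | 12% | – | 99/75/48% |
| PP, outcomes immediate | 29.8% | 12.5% | – | 99/76/49% |
| PP, 12 per arm unobserved | 17.8% | 11.2% | – | 99/74/45% |
| All enrolled, outcomes immediate | 42.7% | 12.7% | 31.2% | 99/69/42% |
| All enrolled, 12 per arm unobserved | 29.6% | 13.4% | 28.4% | 99/71/41% |

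A second simulation of 20,000 trials, with a normal approximation to the posteriors, found the final PP test failing in 29–31% of success-stopped trials when CAE30 is run on all enrolled patients, against 0–1% when it is run on PP. The mechanism shows at equal observed rates near 20%: 55/275 per arm gives a posterior probability of 0.998, which passes 0.985; 28/138 per arm gives 0.981, which fails.

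**The case against.** The strongest reply is that the population is not in doubt. SAP 2.3.3 says interim CAE30 non-inferiority is on PP, Table 2.6 counts PP patients at each look, and 350 enrolled per arm in step 3 is compatible with about 175 PP. On that view the all-patient figures describe an error against the SAP. The success rule refers to patients already enrolled, so with PP and no future patients it is computed correctly.

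This stands as a limit: the success-stop harm and the lowest futility rates arise only if an analyst follows SAP 2.5 literally and passes over SAP 2.3.3. It does not rescue step 1a. With PP data in hand, 350 minus enrolled still adds about twice the expected PP patients, and no text says how to predict PP status.

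Three further limits also stand. Futility is advisory, and three PCT counts flip in the example, the last at 0.101 against a cut-off of 0.1. When PCT is truly worse by the margin (25% vs 15%), futility at 550/650 is 83/94% on the hybrid reading and 90/96% on PP, so that signal largely survives. The low end of the success-stop range (17.8% at 550 on PP) treats incomplete patients as wholly unobserved and falls short of the table's 27%; the two extremes bracket that figure.

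**Conclusion.** The concern holds and should be fixed. As written, SAP 2.5 does not implement the design behind γ = 0.985 and Table 2.6.

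- An analyst who infers PP but follows step 1a gives futility advice in about half as many trials at 550 as intended, and in about three quarters as many at 650.
- One who applies the recipe to all patients almost never gives that advice in the planning scenario.
- If the binding success stop takes CAE30 on all enrolled patients, more than a quarter of the stops at 550 leave the PP test unmet, at a cost of about 5 points of CAE30 power (3 to 7 across the two follow-up extremes).

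These sizes rest on the SAP's planning rates and on PP being a random half of patients. No inflation of type I error is claimed: futility is non-binding, and simulated shortABx error stayed at about 2.3% on either reading.

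**What to change.** Amend SAP 2.5, steps 1a, 1b, 2 and 3:

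- Compute CAE30 predictive probabilities from interim PP counts.
- Predict the PP status of future patients, and of patients with incomplete follow-up, from the observed PP fraction in each arm with its uncertainty, for example beta-binomially. Of 75 future patients per arm, about 38 would be PP (95% range 28 to 47). The fraction should be arm-specific because SAP 3.1 sets different criteria by arm: stewardship and algorithm adherence in the PCT arm, and "if assigned to control group, no PCT measurements to treating physician during index hospitalization" in the control arm. Carrying the uncertainty matters little numerically: with 34 vs 28 events of 138 the predictive probability is 0.044, against 0.041 with the fraction fixed.
- Evaluate success at the projected PP size.
- For the success stop, state that the component for patients yet to be enrolled is dropped for all three endpoints, with CAE30 on enrolled PP patients and shortABx and prescribedABx on enrolled ITT patients.

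The cost is a few lines of text, with no patients and no additional data. The PP projection is the one that reproduces Table 2.6, so no new design simulation is needed.
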